## 4.0 OBJECTIVES

### 4.1 Primary

**4.1.1** To determine the feasibility of administering the amino acid leucine and to determine the pharmacokinetics of leucine administration in patients with Diamond Blackfan anemia (DBA) who are red cell transfusion-dependent.

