## 15.0 WITHDRAWAL AND OFF STUDY CRITERIA

**15.1 Subject's choice:** A subject may withdraw from the study at any time. The risk of withdrawing will be discussed, as will alternative treatment options. Once off study, subjects will be referred back to his or her referring physician. Alternative treatment will then be discussed with the primary hematologist.

**15.2 PI Decision:** Alternative treatment options will be discussed with the subject, who will then be referred back to his or her referring physician.

**15.3 Discontinuation for Toxicity:** Subjects will be discontinued from study for any Grade III/IV toxicity related to the study drug as determined by PI.

**15.4 Discontinuation for Non-Adherence:** Subjects will be discontinued from study if non-adherent to protocol.

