### 16.2 Specific Statistical Aims of the Study (for the Data Analysis)

**16.2.1** The primary objective of the study is to estimate the proportion of complete responders, partial responders or non-responders at 9 months. These proportions will also be estimated at 6 months.

**16.2.2** To determine the time-to-first occurrence of a CR or PR. Subjects who do not achieve CR or PR by the end of the study at 9 months will be considered 'censored for CR (PR)'.

**16.2.3** To catalogue the phenotypic characteristics of the responders and non-responders at 6 and 9 months.

**16.2.4** To examine the frequency and severity of adverse events (AEs) that may arise from the study and to determine if these AEs are related to the study drug.

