### 16.3 Endpoint Variables

The primary outcome is the type of response observed at 9 months (and 6 months). Response to treatment can be one of the following:

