# Master Protocol

- a. Complete response (CR): Hb > 9 gm/dL and transfusion-independence as defined in DBA
- b. Partial response (PR): Hb < 9 gm/dL and increased reticulocyte count to greater than 1% and any increase in transfusion interval from baseline. (Baseline reticulocytes range from 0.1 to 0.5 and transfusions are usually performed every 3 weeks. An increase of reticulocyte counts to over 1 to 1.5% and any increase in transfusion interval will be considered a PR.)
- c. No response (NR): no change in transfusion requirements and no significant change in Hb or reticulocytes (or any response that does not satisfy the conditions of either a PR or CR)
- d. Progression: worsening of disease as defined by the need for more frequent transfusions

Secondary outcomes include time-to-occurrence of either a PR or CR, and safety parameters such as type, frequency, and severity of adverse events and relationship to leucine (according to the NCI CTCAE version 4.0).

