## 16.4 Statistical Methods

This is a standard Phase I/II study with the goal of determining the feasibility, safety and efficacy of the use of leucine in transfusion-dependent DBA subjects. A maximum of 50 subjects will be enrolled into the study. The statistical approach will be primarily descriptive in nature.

For specific aim 1, the proportion of subjects achieving a specific response at 6 and 9 months (CR, PR, NR or progression) along with their corresponding 95% confidence intervals, will be calculated using standard methods of estimating proportions.

For specific aim 2, time-to-response (separately for CR and PR) will be analyzed using survival analysis techniques. Subjects who do not achieve CR or PR by the end of the study at 9 months will be considered 'censored for CR (PR)'. Kaplan-Meier curves will be generated and the log-rank test will be used for any comparisons with respect to time-to-CR (PR), if feasible.

For specific aim 3, the approach will be primarily descriptive. However, we may carry out some analyses if feasible. First, response status at 9 months (separately for CR and PR) will be cross-tabulated with certain subject phenotypes; a chi-square test or Fisher's exact test, as appropriate, will be used to determine if there is an association between response status and the certain phenotype. Second, time-to-response will be analyzed. Kaplan-Meier curves will be generated and the log-rank test will be used to compare phenotypes with respect to time-to-CR (PR), if feasible. Subjects who do not achieve CR or PR by the end of the study at 9 months will be considered 'censored for CR (PR)'.

For specific aim 4, the proportion of adverse events will be tabulated and their corresponding 95% confidence interval will be calculated.

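### Section 15.4 takes non-adherent subjects off study without defining non-adherence, and section 16 does not say how they count, so the 9-month response rate may be computed in adherers only

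*Combined protocol and SAP*

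**What the plan says.** Section 15.4, under the withdrawal and off-study criteria, reads: "Subjects will be discontinued from study if non-adherent to protocol". It gives no threshold, measure or assessment time for non-adherence, and it covers the whole protocol, not only the capsules.

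Feasibility comes first among the primary objectives in 4.1.1, "To determine the feasibility of administering the amino acid leucine and to determine the pharmacokinetics of leucine administration", and is repeated in 8.1 and 16.1.1. Section 16.4 again gives the trial "the goal of determining the feasibility, safety and efficacy of the use of leucine in transfusion-dependent DBA subjects".

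The statistical aims are different. Section 16.2.1 says: "The primary objective of the study is to estimate the proportion of complete responders, partial responders or non-responders at 9 months". Section 16.3 says: "The primary outcome is the type of response observed at 9 months (and 6 months"). Section 16.4 will estimate "the proportion of subjects achieving a specific response at 6 and 9 months (CR, PR, NR or progression"), without naming an analysis set. The no-response category in 16.3 has a catch-all: "or any response that does not satisfy the conditions of either a PR or CR".

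Once participation has stopped, the only collection stated to continue is SAE reporting, for 12 weeks (18.4.8).

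**The concern.** Keeping up a three-times-daily regimen for 9 months, in subjects from age 2, is a large part of what feasibility means here. Section 15.4 ends observation of a subject at the point where that subject supplies negative evidence on the first primary objective. Response is scored on study at 6 and 9 months (14.1), so someone removed at month 4, for example, has neither assessment.

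The rule thus selects on something that happens after enrolment and may well be related to outcome. In an open-label trial, subjects who see no benefit could be the ones who stop taking capsules. The documents do not say so, but the plan should not depend on its being untrue. Section 16.5 expects these results to help set the effect size for a Phase III trial, so an inflated rate would carry forward.

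**Working it through.** **Inputs.** Maximum of 50 subjects (16.4); two-sided 95% interval by the normal approximation (16.5). The documents give no non-adherence rate, so d = 10% to 40% is assumed. For illustration I also assume 10 responders, all adherent.

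**The plan's own figure.** Half-width = 1.96 × √(0.5 × 0.5 / 50) = 0.1386, giving 36.1% to 63.9%. This matches the stated ±13.9 points. It needs all 50 subjects in the denominator and makes no allowance for discontinuations.

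**If removed subjects leave the denominator.** The number remaining is m = 50(1 − d). The rate becomes 10/m instead of 10/50, an inflation of 1/(1 − d). The maximum half-width becomes 1.96 × √(0.25/m). The intervals for the rates are exact (Clopper-Pearson).

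| d | m | Rate (exact 95% CI) | Inflation | Maximum half-width, points |
|---|---|---|---|---|
| 0% | 50 | 20.0% (10.0 to 33.7) | 1.00 | 13.9 |
| 10% | 45 | 22.2% (11.2 to 37.1) | 1.11 | 14.6 |
| 20% | 40 | 25.0% (12.7 to 41.2) | 1.25 | 15.5 |
| 30% | 35 | 28.6% (14.6 to 46.3) | 1.43 | 16.6 |
| 40% | 30 | 33.3% (17.3 to 52.8) | 1.67 | 17.9 |

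**If removed subjects count as non-responders.** The rate stays at 10/50 = 20.0% and the stated precision stands. The text does not choose between these two treatments.

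**Feasibility.** With 10 of 50 non-adherent, the proportion over all enrolled is 20.0% (10.0% to 33.7%). A table of retained subjects only would show 0/40, with an upper limit of 8.8%. Section 16 specifies neither table.

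**Time to response.** Sections 16.2.2 and 16.4 censor subjects who have not responded by the end of the study at 9 months. They set no censoring time for someone who leaves earlier.

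**The case against.** A reader might infer that 15.4 deletes these subjects from the data and that efficacy is read in adherers only. The documents do not support that. Section 15.4 governs participation, not the analysis set, and nothing removes discontinued subjects from the denominator. Several places point the other way: 16.4 speaks of subjects with no evaluable or per-protocol restriction, 16.5 bases precision on 50, accrual closes at 50 enrolled with no replacement described (11.1.1), and the catch-all in 16.3 could put removed subjects in the no-response category. A removal under 15.4 could also itself be counted as a feasibility failure.

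This limits the claim but does not remove it. The catch-all mentions neither discontinuation nor missing assessments. The parallel definition in 14.1.3 lacks it and requires no change in transfusion needs, hemoglobin or reticulocytes, which cannot be shown without data. No text plans to report removals as a feasibility result.

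A reader might also infer that one missed dose triggers removal. That is strained: 13.5.3 allows drug to be interrupted for an SAE, with removal tied to possible relatedness, and 18.3.3 has certain deviations reported without mention of removal. The absence of a definition is the fair criticism. Nor can one conclude that adherence goes unrecorded: the case report form (Appendix G) is not among the pages available, and 18.2.1 includes drug accountability in monitoring. On burden, 13.1.3 allows capsules to be mixed into food or dissolved in liquids.

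**Conclusion.** The point holds as a gap with a possible bias, not as a demonstrated one. Non-adherent subjects leave observation under an undefined rule, their primary outcome is then not collected, and section 16 does not say how they enter the response proportions or the censoring. Feasibility has no measure.

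The inflation of 1.11 to 1.67, and the half-widths of 14.6 to 17.9 points against the stated 13.9, rest on three assumptions: non-adherence of 10% to 40%, all responders adherent, and removed subjects dropped from the denominator. If they are counted as non-responders, the rate is not inflated and 13.9 points stands. Even then, their actual response at 6 and 9 months is unobserved and feasibility remains unmeasured. The change is worth making because it is cheap and settles the reading before data are seen.

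**What to change.** **Section 15.4.** Separate stopping study drug from ending study participation, and define non-adherence. For a subject found non-adherent, record the date and reason. Unless consent is withdrawn (15.1), keep collecting hemoglobin, reticulocyte and transfusion data to month 9 and classify response. Whether leucine continues, and how other protocol non-adherence such as prohibited DBA therapy is managed, is for the sponsor and investigator to decide.

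**Section 16.4.** Use all enrolled subjects as the denominator. Count those without a documented complete or partial response as non-responders. Censor time to response at the last assessment; continued collection also means relying less on the assumption that early censoring is unrelated to response. Report the proportion of enrolled subjects who become non-adherent, with a 95% confidence interval and reasons, as a feasibility result. A response rate in adherers may be shown as supportive.

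**Cost.** Short changes to two sections, a reason code on the case report form if it has none, some forms completed for subjects off drug, and a possibly lower headline rate. Section 12.2.2 already describes blood and reticulocyte counts as standard of care for these subjects, and transfusion history is already collected (12.2.3), so the added burden is small.

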## 16.0 BIOSTATISTICAL CONSIDERATIONS

Response to treatment (Complete, Partial, None, Progression) will be evaluated at 6 and 9 months. Time-to-achieve a complete or partial response will be examined as well.

### 16.1 General Study Objectives

**16.1.1** To determine the feasibility of administering the amino acid leucine and to determine the pharmacokinetics of leucine administration in subjects with Diamond Blackfan anemia (DBA) who are red cell transfusion-dependent.

**16.1.2** To determine the efficacy of leucine to produce a hematologic response in subjects with DBA.

**16.1.3** To determine the side effects of leucine administration in DBA subjects (monthly).

**16.1.4** To determine if subjects with DBA are deficient in branched chain amino acids (baseline).

### 16.2 Specific Statistical Aims of the Study (for the Data Analysis)

**16.2.1** The primary objective of the study is to estimate the proportion of complete responders, partial responders or non-responders at 9 months. These proportions will also be estimated at 6 months.

**16.2.2** To determine the time-to-first occurrence of a CR or PR. Subjects who do not achieve CR or PR by the end of the study at 9 months will be considered 'censored for CR (PR)'.

**16.2.3** To catalogue the phenotypic characteristics of the responders and non-responders at 6 and 9 months.

**16.2.4** To examine the frequency and severity of adverse events (AEs) that may arise from the study and to determine if these AEs are related to the study drug.

### 16.3 Endpoint Variables

The primary outcome is the type of response observed at 9 months (and 6 months). Response to treatment can be one of the following:

# Master Protocol

- a. Complete response (CR): Hb > 9 gm/dL and transfusion-independence as defined in DBA
- b. Partial response (PR): Hb < 9 gm/dL and increased reticulocyte count to greater than 1% and any increase in transfusion interval from baseline. (Baseline reticulocytes range from 0.1 to 0.5 and transfusions are usually performed every 3 weeks. An increase of reticulocyte counts to over 1 to 1.5% and any increase in transfusion interval will be considered a PR.)
- c. No response (NR): no change in transfusion requirements and no significant change in Hb or reticulocytes (or any response that does not satisfy the conditions of either a PR or CR)
- d. Progression: worsening of disease as defined by the need for more frequent transfusions

Secondary outcomes include time-to-occurrence of either a PR or CR, and safety parameters such as type, frequency, and severity of adverse events and relationship to leucine (according to the NCI CTCAE version 4.0).

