# Master Protocol

## **12.2 Case Report Form Data (Appendix G)**

The Case Report Form data is to be collected at baseline, at Weeks 2 and 4 and at Months 2, 3, 4, 5, 6, 7, 8, and 9 (or at time of transfusion, except where indicated otherwise). Each visit can be +/- 1 week of the requested time except week 2. Blood drawings can also be +/- 1 week of the requested time except week 2.

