# Master Protocol

**14.1.2 Partial Response (PR)** - Hb < 9 gm/dL with an increase in reticulocyte count to 1% and any transfusion interval increase

**14.1.3 No Response (NR)** - No change in transfusion needs, no change in Hb or reticulocyte count

**14.1.4 Progression** - An increased transfusion requirement with increased volume or increased interval

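### The response categories for the primary outcome contradict each other for a still-transfused subject with Hb of 9 gm/dL or more, reticulocytes above 1% and a longer transfusion interval

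*Combined protocol and SAP*

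**What the plan says.** Section 16.3 makes the type of response at 9 months the primary outcome, with 6 months alongside. Section 16.4 analyses it as the proportion in each category with a 95% confidence interval, in at most 50 subjects. The rules are these:

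- **CR, 16.3a:** Hb above 9 "gm/dL and transfusion-independence as defined in DBA". Section 14.1.1 likewise requires Hb above 9 and an end to transfusion.
- **PR, 16.3b, lead sentence:** "Hb < 9 gm/dL and increased reticulocyte count to greater than 1% and any increase in transfusion interval from baseline".
- **PR, 16.3b, bracketed text:** "An increase of reticulocyte counts to over 1 to 1.5% and any increase in transfusion interval will be considered a PR". No Hb limit is named here.
- **PR, 14.1.2:** "Hb < 9 gm/dL with an increase in reticulocyte count to 1% and any transfusion interval increase".
- **NR, 16.3c:** no change in transfusion needs and no significant change in Hb or reticulocytes, "or any response that does not satisfy the conditions of either a PR or CR".
- **NR, 14.1.3:** no change only, with no residual clause.
- **Progression:** more frequent transfusion (16.3d) or an increased transfusion requirement (14.1.4).

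On timing, section 12.2 collects data at set weeks and months, within 1 week except at week 2, "or at time of transfusion, except where indicated otherwise". Neither 14.1 nor 16.3 says where in the transfusion cycle the response Hb is to be read.

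**The concern.** Among subjects who are still transfused, PR needs no upper limit on Hb to keep it apart from CR, because CR already requires freedom from transfusion. The limit only removes from PR a subject who meets both of its other conditions, and the residual clause in 16.3c then places that subject with those who did not respond.

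The state can arise under the plan's own rules. Section 13.2.2 holds transfusion in a stable subject with Hb above 8 and reticulocytes above 0.5% (or baseline). A subject whose interval is lengthening can therefore be seen at Hb of 9 or more. Donor cells also raise Hb after each transfusion, and the plan does not fix the reading to a pre-transfusion sample.

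Four results depend on the choice of rule: the PR proportion, the NR proportion, time to PR (aim 2) and the cross-tabulation of response with phenotype (aim 3). Section 16.5 also expects the study to help in estimating an effect size for later Phase III trials.

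**Working it through.** **1. The plan's own figure.** Section 16.5 gives a maximum half-width of 13.9 points for n = 50. Check: 1.96 × √(0.5 × 0.5 / 50) = 1.96 × 0.0707 = 0.1386, that is 36.1% to 63.9%. It reproduces. It is a worst case over all proportions, so this point does not affect it.

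**2. The rules applied to one subject.** Inputs: reticulocytes 1.6% (above every cut-off in the text), interval longer than baseline, no increase in transfusion requirement (so not progression). Only Hb and transfusion status vary.

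| Hb (gm/dL) | Transfusion status | 16.3 lead text plus 16.3c | 16.3b bracketed text | 14.1 |
|---|---|---|---|---|
| 7.5, 8.5, 8.9 | still transfused | PR | PR | PR |
| 9.0 | still transfused | NR | PR | none |
| 9.1, 9.5, 10 | still transfused | NR | PR | none |
| 8.9 | off transfusion | PR | PR | PR |
| 9.0 | off transfusion | NR | PR | none |
| 9.1 | off transfusion | CR | CR | CR |

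The off-transfusion rows count freedom from transfusion as a longer interval. Below Hb 9 the three readings agree. From 9 upward, in a still-transfused subject, they give three different answers. Off transfusion, the lead text runs PR, NR, CR as Hb goes 8.9, 9.0, 9.1.

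**3. Reticulocyte cut-offs.** Three are stated: reaching 1% (14.1.2), above 1% (16.3b lead sentence) and over 1 to 1.5% (16.3b bracketed text). A value of 1.2%, for example, clears the first two and is uncertain under the third.

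**4. Size per subject.** One subject in 50 is 1/50 = 2 percentage points. The documents give no expected response rate, so the following counts are assumed for illustration, with interval p ± 1.96 × √(p(1 − p)/50):

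- 5/50 responders (CR or PR): 10%, half-width 1.96 × √(0.1 × 0.9/50) = 8.3 points, interval 1.7% to 18.3%.
- 5 disputed subjects scored PR instead of NR, 10/50: 20%, half-width 1.96 × √(0.2 × 0.8/50) = 11.1 points, interval 8.9% to 31.1%.
- 1, 3 or 10 disputed subjects: 6/50 = 12%, 8/50 = 16%, 15/50 = 30%.

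**5. Time to PR.** Section 16.4 censors at 9 months a subject who never meets PR. Under the lead text a disputed subject is censored, or has the PR dated later, at a visit where Hb is below 9.

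**The case against.** The strongest reply is that the bracketed text in 16.3b already gives the sensible answer. It scores the disputed subject PR, and the residual clause in 16.3c then never applies. This stands as far as it goes: a reader might infer that the plan definitely scores such subjects NR, and the documents do not support that. They support a contradiction within one bullet, plus a gap in 14.1, where the residual clause is absent. The bracketed text does not resolve it, because 14.1.2 and the lead sentence both carry the Hb limit and nothing says which text governs.

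A reader might also infer that the primary analysis ranks better subjects below worse ones. It does not: section 16.4 estimates proportions descriptively and ranks no one. Nor is a higher Hb in a transfused subject necessarily a better state, since it may reflect the point in the cycle. The effect is misclassification.

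A third tempting step is to estimate how many partial responders would be lost, by modelling the fall of Hb after a transfusion. The documents give no post-transfusion Hb, no rate of decline and no expected PR rate. Section 12.2 allows collection at the time of transfusion, and the hold rules in 13.2 act on Hb, which points towards pre-transfusion readings. If all of these were lows below 9, the loss would be near zero. No percentage lost can be defended.

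Finally, this is a descriptive pilot with a convenience sample, and Hb, reticulocytes and transfusions are all recorded, so subjects can be re-scored. That makes the repair cheap. It does not settle which rule the primary result uses.

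**Conclusion.** The point holds as a contradiction and a gap in the primary outcome definition. For a still-transfused subject with Hb of 9 or more, reticulocytes above every stated cut-off and a longer interval, the plan gives NR, PR or no category, depending on which sentence is applied. Hb of exactly 9.0 meets neither CR nor PR under the lead definitions or 14.1, whether or not the subject is transfused.

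If the lead definitions are applied, the PR proportion is understated, NR is overstated, PR events are late or missing, and some responders sit among the non-responders in the phenotype comparison. The size is 2 points per affected subject at 50 subjects. How many are affected cannot be derived; it depends on when Hb is read, and ranges down to near zero if every reading is a pre-transfusion low below 9. The conclusion itself rests only on the wording of 14.1 and 16.3. Because it governs the primary outcome, it should be settled before any subject is scored.

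**What to change.** 1. In 14.1.2 and 16.3b, delete the condition that Hb be below 9. PR then means: CR not met, reticulocytes above one cut-off, and a transfusion interval longer than baseline, at any Hb. This agrees with the bracketed text of 16.3b on the Hb limit.
2. Choose one reticulocyte cut-off and use it in both sections.
3. Define NR in both sections as not CR, PR or progression. A subject who meets only one of the two PR conditions, such as a longer interval with reticulocytes of 0.8%, then has a category.
4. State whether Hb of exactly 9.0 satisfies CR.
5. State which Hb reading, relative to transfusion, is used at 6 and 9 months. CR needs this even after the Hb limit is removed from PR.

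The cost is a text change in two sections. No new data are needed, because Hb, reticulocytes and transfusion dates and volumes are already collected. The downside is that the PR rate no longer follows the current 9 gm/dL wording; a sensitivity table under the current lead definition would show how far the choice matters.

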## 13.2 Transfusion Therapy During Study Drug Administration

Subjects will receive 10-15 ml/kg/transfusion, with all volumes recorded on the Case Report Forms.

**13.2.1 If the hemoglobin (Hb) is less than 8 gm/dL and there is no evidence of reticulocyte response (retic count < 0.5%), the subject will be transfused as usual.**

**13.2.2 If the Hb is greater than 8 gm/dL, the reticulocyte count is greater than 0.5% (or baseline) and the subject is clinically stable (without fever, respiratory illness, etc.), the transfusion should be held.** The subject should be followed again in 1-2 weeks and reassessment will be made to see if a response is occurring.

**13.2.3 If the Hb is between 7-8 gm/dL, the reticulocyte count is greater than 0.5% (or baseline), and the subject is clinically stable, then the subject can opt out of transfusion, based upon clinical considerations, for one week, or receive 10 ml/kg packed red blood cell transfusion so as not to**

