# Master Protocol

abort a possible response. If the subject continues to show a response then Hb can be checked every 2 weeks and transfusion held. If not, the subject will resume the transfusion schedule.

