## 14.0 EVALUATION CRITERIA

### 14.1 On-Study Response Criteria - evaluated at 6 and 9 months of treatment

#### 14.1.1 Complete Response (CR) – Hb $> 9$ gm/dL and weaned off of transfusion therapy

1a- Complete response lasting  $\geq 6$  months

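### A subject off transfusion with Hb of 9 or less and reticulocytes of 1% or less is scored No Response under Section 16.3 and fits no category under Section 14.1

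*Combined protocol and SAP*

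**What the plan says.** Section 16.3 (Endpoint Variables) makes response type at 9 months, and also at 6 months, the primary outcome. Its four categories are:

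- CR: Hb above 9 g/dL and transfusion independence.
- PR: Hb below 9 g/dL with "increased reticulocyte count to greater than 1% and any increase in transfusion interval from baseline". A note gives baseline reticulocytes as 0.1 to 0.5 and the usual interval as 3 weeks.
- NR: transfusion need unchanged and Hb or reticulocytes not materially changed, extended by the bracket "or any response that does not satisfy the conditions of either a PR or CR".
- Progression: transfusions needed more often.

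Section 14.1 (On-Study Response Criteria) defines the same four categories with differences. CR is Hb above 9 "and weaned off of transfusion therapy". PR asks for reticulocytes rising to 1%, where 16.3 asks for more than 1%. NR is no change in transfusion need, Hb or reticulocytes, with no catch-all.

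Section 13.2 governs transfusion on study. Under 13.2.2, once Hb is above 8 g/dL and "the reticulocyte count is greater than 0.5% (or baseline) and the subject is clinically stable (without fever, respiratory illness, etc.), the transfusion should be held". A further visit follows after 1-2 weeks, at which "reassessment will be made to see if a response is occurring". Section 13.2.3, which covers Hb 7-8, leads on to: "If the subject continues to show a response then Hb can be checked every 2 weeks and transfusion held".

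**The concern.** The catch-all puts into NR some subjects whose transfusion need has fallen, even to nothing. That contradicts the description with which NR opens. It also sits badly with the rest of the protocol. Section 7.0 counts two earlier patients as partial responders because their time between transfusions lengthened, and mentions no reticulocyte condition. Section 19.4.1 names fewer or no transfusions as the benefit hoped for.

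The filing affects three analyses. It lowers the response proportions and raises the NR proportion at 6 and 9 months (aim 1). A subject who never meets CR or PR is censored in the time-to-response curves (aim 2). The subject is also described with the non-responders in the phenotype comparison (aim 3), which is meant to find out who benefits.

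**Working it through.** **The plan's own figure.** Section 16.5 gives 50% ± 13.9% as the widest 95% interval at n = 50. Check: 1.96 × √(0.5 × 0.5 / 50) = 0.1386, so 36.1% to 63.9%. The figure is reproduced, and this point does not affect it.

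**Classification check.** The rules of 16.3 and 14.1 were applied literally to test records. Being off transfusion was counted as a longer interval, the reading most favourable to PR. Reticulocytes rising to 1% in 14.1.2 was read as 1% or more. In every record reticulocytes are above the stated baseline range of 0.1 to 0.5.

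| Record | Transfusion status | Hb (g/dL) | Reticulocytes | Section 16.3 | Section 14.1 |
|---|---|---|---|---|---|
| 1 | off transfusion | 8.5 | 0.8% | NR | no category |
| 2 | off transfusion | 8.9 | 1.0% | NR | PR |
| 3 | off transfusion | 8.5 | 1.2% | PR | PR |
| 4 | still transfused, longer interval | 7.8 | 1.2% | PR | PR |
| 5 | still transfused, longer interval | 7.8 | 0.8% | NR | no category |

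- Record 1 fails CR because 8.5 is not above 9, and fails PR because 0.8% is not above 1%. It is not progression, because transfusion need fell. Under 16.3 only the catch-all is left. Under 14.1 NR does not fit either, because transfusion need and reticulocytes both changed.
- Record 2 shows the two sections giving different answers at exactly 1%.
- Record 4 ranks above record 1 although it still needs transfusion. Record 5 shows that a longer interval alone does not produce this reversal. The comparator must also have reticulocytes above 1% and Hb below 9.

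**Can the protocol lead to record 1?** Yes. Hb 8.5 and reticulocytes 0.8% in a stable subject meet the 13.2.2 condition for holding a transfusion, which requires neither Hb above 9 nor reticulocytes above 1%.

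**Size.** Each such subject is 1/50 = 2.0 percentage points. The number of such subjects is not given. As an assumed illustration only, suppose 5/50 = 10% are scored CR or PR. The Wald interval is 0.10 ± 1.96 × √(0.10 × 0.90 / 50) = 0.10 ± 0.083, or 1.7% to 18.3%. By the same formula, counting further subjects as responders gives:

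| Added | Responders | Proportion | 95% interval (Wald) |
|---|---|---|---|
| 1 | 6/50 | 12% | 3.0% to 21.0% |
| 3 | 8/50 | 16% | 5.8% to 26.2% |
| 5 | 10/50 | 20% | 8.9% to 31.1% |

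**The case against.** The reticulocyte condition looks deliberate. Section 16.3 states it twice and sets it against a baseline range. It also has a purpose: the trial is open-label, and 13.2.2 itself directs that transfusions be held, so the management rule alone can lengthen an interval. A laboratory condition guards against scoring that as a drug effect. This stands, and it is why such subjects should not simply be relabelled PR. It does not justify filing them under a category described as unchanged transfusion need.

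A reader might infer that 13.2 sets a second, lower response threshold of 0.5%, so that subjects the protocol calls responders are scored as failures. The text does not support this. Section 13.2.2 holds the transfusion in order to find out whether a response is occurring. The wording about a continuing response closes 13.2.3 and carries no threshold. If *response* there means the 14.1 or 16.3 response, a subject at 0.8% might return to scheduled transfusion, and a long hold might be uncommon. What can be said is that the word is undefined in 13.2.

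A reader might also infer a known downward bias in the response rate. That would need the frequency of this profile, which the documents do not give, and a decision that a different definition of response is the true one.

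Finally, the analysis is mainly descriptive and not formally powered, so no test decision turns on this. That limits the consequence, but the response proportions are still the trial's primary result.

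**Conclusion.** The point holds as a classification fault in the primary outcome. Read literally, 16.3 scores a subject off transfusion with Hb of 9 or less and reticulocytes of 1% or less as NR, against that category's own description. Section 14.1 leaves the same subject unclassified, except that at exactly 1% with Hb below 9 it gives PR. A still-transfused subject ranks higher only if reticulocytes exceed 1%, Hb is below 9 and the interval is longer.

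The size is 2 percentage points per subject with 50 analysed, plus censoring in aim 2 and placement with the non-responders in aim 3. The total effect is unknown, and the illustration above rests on assumed counts. The conclusion itself needs no assumption beyond a literal reading of the two sections.

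**What to change.** 1. Replace the lists in 14.1 and 16.3 with one set of mutually exclusive and exhaustive categories, using a single reticulocyte cut-off chosen by the investigators and stated identically in both places.
2. Limit the NR catch-all to subjects with no reduction in transfusion need.
3. Pre-specify a separate row, with its 95% confidence interval, for subjects who are transfusion-free or have a longer interval but do not meet the Hb or reticulocyte condition. Report the response proportion with and without the transfusion-free subjects in that row.
4. Reconcile the undefined word *response* in 13.2 with 14.1 and 16.3. This is a request for consistent wording; no transfusion threshold need change.

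The cost is wording in these sections and one more category in a descriptive table. Hb and reticulocytes are already scheduled at every visit, and transfusion dates and volumes are already recorded.
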